2.3.2. Benefit Assessment

This is a healthy participant study and there is no direct benefit to study participants.

2.3.3. Overall Benefit: Risk Conclusion

Taking into account the measures implemented to minimize risk to participants in this study, the potential risks identified in association with ALXN1840 are justified by the anticipated benefits that may be afforded to patients with WD.

3. OBJECTIVES AND ENDPOINTS

Table 4: Mapping Objectives to Endpoints/Estimands

Objective	Endpoints/Estimands
Primary	
To assess the relative bioavailability of equal doses of ALXN1840 administered as 1.25 mg EC mini-tablets versus a single 15 mg EC tablet	PK parameters for plasma total Mo and PUF Mo (C_{max} , AUC_t , and AUC_{∞})
Secondary	
To assess dose-proportionality between 2.5 mg (2×1.25 mg), 5 mg (4×1.25 mg), 10 mg (8×1.25 mg), 15 mg (12×1.25 mg), and 30 mg (24×1.25 mg) EC mini-tablet doses	Dose-normalized PK parameters for plasma total Mo and PUF Mo (C_{max_n} , AUC_{t_n} , and AUC_{∞_n})
Safety	
To assess the overall safety and tolerability of ALXN1840, administered as 1.25 mg EC mini-tablets and as a single 15 mg EC tablet	Incidence of TEAEs and TESAEs, physical examination, vital signs measurements, clinical laboratory, and 12-lead ECG results
Exploratory	
To explore relationships between total and PUF Mo clearance and body size — body weight (kg) and BMI (kg/m^2)	CL/F, body weight, and BMI
To explore PD of ALXN1840 either as a single 15 mg EC tablet or EC mini-tablets of 1.25 mg at different total dose strengths	Absolute and percent changes from pre-dose baseline of plasma Cu concentrations: total and PUF Cu

Abbreviations: AUC_{∞} = area under the plasma concentration versus time curve from time 0 to infinity; AUC_t = area under the plasma concentration versus time curve from time 0 to the last quantifiable concentration; BMI = body mass index; CL/F = apparent oral clearance; C_{max} = maximum observed concentration; Cu = copper; EC = enteric-coated; ECG = electrocardiogram; Mo = molybdenum; n = dose-normalized; PD = pharmacodynamic(s); PK = pharmacokinetic(s); PUF = plasma ultrafiltrate; TEAE = treatment emergent adverse events; TESAE = treatment emergent serious adverse event.

4. STUDY DESIGN

4.1. Overall Design

This is a Phase 1 study to compare the relative bioavailability of 2 formulations of ALXN1840 in healthy participants. Equal doses of the 1.25 mg EC mini-tablet will be compared with a single 15 mg EC tablet (12×1.25 mg and 1×15 mg, respectively). The study will be conducted in 2 periods. The study will also assess dose-proportionality between 2.5 mg (2×1.25 mg), 5 mg (4×1.25 mg), 10 mg (8×1.25 mg), 15 mg (12×1.25 mg), and 30 mg (24×1.25 mg) EC minitab doses in the Dose-Proportionality Extension Period.

The study has a Screening Period (Days -28 to -2), the Two-way Crossover Period, consisting of 2 dosing periods (Day 1 to Day 11 each), and a Dose-Proportionality Extension Period of 14 days. After completing the Screening Period, enrolled participants will be admitted to the clinical research unit (CRU) on Day -1 for dosing on Day 1 in Dosing Period 1. If discharged after Dosing Period 1, participants will be readmitted to the CRU for Dosing Period 2 following a minimum washout of 14 days after the previous dose, and again for the Dose-Proportionality Extension Period after a minimum washout of 14 days.

This study will be conducted with approximately 48 healthy participants enrolled to allow for a minimum of 40 participants to complete the Dose-Proportionality Extension Period of the study.

Two-way Crossover Period

The Two-way Crossover Period is a randomized, open-label, two-way (2-period, 2-sequence) crossover design to assess the relative bioavailability of 12×1.25 mg EC mini-tablets compared with the 15 mg EC tablet currently used in clinical studies. Participants will be randomized to one of the 2 treatments sequences. Randomized treatment assignment will be based on Baseline body mass index (BMI). Two strata for Baseline BMI (< 25 , 25 to < 32 kg/m²) will be used:

- Treatment A: ALXN1840 12×1.25 mg EC mini-tablets
- Treatment B: ALXN1840 single 15 mg EC tablet (reference tablet, currently being tested in the Phase 3 Study WTX101-301)

Blood samples for PK analysis of total and PUF molybdenum (Mo) (as surrogate measures of ALXN1840 PK) and PD/biomarkers will be collected in each dosing period on Day 1 at pre-dose, and postdose at 1, 2, 3, 4, 5, 6, 8, 12 and 24 hours (Day 2) and then at 24 hour intervals on Days 3, 4, 5, 6, 7, 8, 9, 10, and 11.

The 336-hour sample for Dosing Period 1 will be collected predose in Dosing Period 2. Participants may be discharged on Day 11 of each dosing period after completion of all procedures and review of all safety data. The end of Dosing Period 2 will occur on Day 15 ± 2 of Dosing Period 2, with the collection of the 336-hour PK sample for Dosing Period 2.

Participants may be asked or required to stay in the CRU during the Two-way Crossover Period, and/or at the end of the Dose-Proportionality Extension Period before the End of Study (EOS) Visit, for their own safety, and also to maintain the integrity of the conduct of the study.

Dose-Proportionality Extension Period

The Dose-Proportionality Extension Period is a re-randomized, open-label, parallel group design to assess the dose-proportionality between 2.5 mg (2×1.25 mg), 5 mg (4×1.25 mg), 10 mg (8×1.25 mg), and 30 mg (24×1.25 mg) EC mini-tablet doses.

The Dose-Proportionality Extension Period will be conducted following completion of the Two-way Crossover Period of the study and after an at least 14-day washout period. Participants will be re-randomized as follows:

- Treatment C (N=10-12): ALXN1840 2.5 mg (2×1.25 mg EC mini-tablets)
- Treatment D (N=10-12): ALXN1840 5 mg (4×1.25 mg EC mini-tablets)
- Treatment E (N=10-12): ALXN1840 10 mg (8×1.25 mg EC mini-tablets)
- Treatment F (N=10-12): ALXN1840 30 mg (24×1.25 mg EC mini-tablets)

The 15 mg dose will not be repeated during the Dose-Proportionality Extension Period. For the purpose of evaluating dose-proportionality of the EC mini-tablet, data obtained from Treatment A of the Two-way Crossover Period (12×1.25 mg EC tablets) will be included to represent a dose of 15 mg.

Re-randomized treatment assignment will be based on body mass index (BMI). Two strata for BMI (< 25 , 25 to < 32 kg/m²) will be used. Block randomization will be used to equally randomly assign participants to each treatment.

4.2. Scientific Rationale for Study Design

This study is being conducted in healthy participants so that the assessments are not confounded by disease activity, comorbidities, or concomitant medications. The inclusion and exclusion criteria for this study are consistent with Phase 1 clinical pharmacology studies that assess the medication of interest and to minimize assignment bias. As the key objectives of the study are assessments of bioavailability and dose-exposure proportionality, a blinded design is not necessary.

The Two-way Crossover Period was adopted to control the variability within and between participants. A minimum of 14 days between dose administration is considered sufficient to eliminate, on average, approximately more than 99.2% of the plasma total Mo.

Following ALXN1840 administration, the active drug moiety tetrathiomolybdate rapidly binds Cu to form the TPC in the liver and blood and presents as such in the systemic circulation. If TPC is not rapidly formed, tetrathiomolybdate spontaneously undergoes serial hydrolysis to form molybdate, the most common form of nutrient Mo, and is excreted in the urine. Total Mo concentration has been measured as a surrogate of ALXN1840 PK; however, total Mo concentration cannot distinguish whether the Mo is complexed with Cu and albumin (as in TPC), free active ALXN1840 drug, intermediate hydrolysis products, or molybdate which may be from ALXN1840 hydrolysis. To better characterize the amount of non-TPC bound ALXN1840 and its degradation products, PUF Mo, which represents the free parent drug (ALXN1840), short-lived intermediate hydrolysis products, and molybdate, will be measured. Total Mo and PUF Mo concentrations also include physiologic molybdate concentrations from dietary micronutrient molybdate intake. While it is not feasible to separate and quantify ALXN1840 directly in the

plasma, total Mo PK and PUF Mo PK provide surrogate measures to characterize ALXN1840 exposure. To better characterize the absorption, distribution, metabolism, and excretion (ADME) of ALXN1840, the PK of both total Mo and PUF Mo will be characterized and described. The primary PK measure is total Mo, whereas PUF Mo is an exploratory measure.

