For patients aged 3 to < 6 years, the population PK modeling results showed that a 5 mg dose has comparable exposure to 15 mg administered to adult patients, and that a 15 mg dose has a higher exposure than 30 mg, but a lower exposure than 60 mg administered to adult patients. Hence, the predicted dose range for patients aged 3 to < 6 years is 5 mg to 15 mg, which is anticipated to provide comparable safety and efficacy outcomes to those in adolescent and adult patients over 12 years of age with a dose range of 15 mg to 60 mg currently allowed in the ongoing Phase 3

Study WTX101-301. Therefore, the EC mini-tablet doses of 2.5, 5, 10, 15, and 30 mg will be tested in this study, which covers the entire anticipated dose range recommended in the planned study in the pediatric population.

An inductively coupled plasma-mass spectroscopy (ICP-MS) method, with a lower limit of quantification (LLOQ) of 1.00 ng/mL and 0.25 ng/mL for the assays of total Mo and PUF Mo, respectively, has been previously implemented for analyzing plasma samples from Study WTX101-HV-106. In that study, for the 15 mg and 60 mg doses, %AUC_{extrap} ranged from 1.3% - 12.2% (all were less than 20%). In the current study, a maximum observed concentration (C_{max}) for total Mo of approximately 40 ng/mL is anticipated after the lowest ALXN1840 dose of 2.5 mg and with an assay LLOQ of 1.00 ng/mL, it would be possible to detect measurable total Mo concentrations at a mean of 1.25 ng/mL for approximately 5 half-lives with reasonably low expectation for excess AUC extrapolation of over 20% for AUC_∞ estimation. A C_{max} for PUF Mo of approximately 2 ng/mL is anticipated after the lowest ALXN1840 dose of 2.5 mg and with an assay LLOQ of 0.25 ng/mL, it would be possible to detect measurable PUF Mo concentrations at a mean of 0.25 ng/mL for approximately 3 half-lives with possibility of AUC extrapolation of over 20% for AUC_∞ estimation.

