8.8. Treatment Compliance

Not Applicable.

This document is confidential.

9. Pharmacokinetics

Pharmacokinetic analyses will be performed using the PKDS-CO and PKDS-E.

PK parameters will be calculated for total and PUF molybdenum (as surrogate measures of ALXN1840 PK) using noncompartmental methods with Phoenix® WinNonlin® (Certara USA Inc., Princeton, New Jersey) Version 8.0 or higher. Calculations of individual PK parameters will be based on measured total molybdenum and, when feasible, PUF molybdenum concentrations and the actual sampling times elapsed from the actual reference dosing time data recorded during the study.

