9.3. Presentation of Concentration Data

9.3.1. Handling of Missing Data

Missing concentration data for all participants who are administered scheduled study treatments will be considered as non-informative missing and will not be imputed. No concentration estimates will be provided for missing sample values.

For the derivation of AUC and for the individual plasma concentration versus time curves, the following rules will apply:

- Concentration values below the assay's lower limit of quantification (BLQ) in pre-dose Day 1 samples will be treated as zero;
- The sampling time of pre-dose samples relative to dosing will also be treated as zero;
- BLQ's between two quantifiable samples will be set to missing;
- The first BLQ after the last measurable sample will be set to missing; any subsequent BLQ's will be set to zero;

For plasma concentration summary the following rules will apply:

- All BLQ values will be set to zero;
- No further imputation will be applied to any missing values.

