9.3.3. Summary of PK Concentrations by Matrix

Plasma concentration data will be summarized separately by time point for each treatment using the following descriptive statistics: number of participants, arithmetic mean, SD, CV, geometric mean, geometric CV, median, minimum, and maximum.

Mean plasma concentration versus scheduled time profiles will be presented in figures on both linear and semilogarithmic scales. Individual plasma concentration versus nominal time profiles will be presented similarly.

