9.4. Derivation of Pharmacokinetic Parameters

- The apparent C_{max} and the corresponding t_{max} along with T_{lag} will be read directly from the concentration-time plot (observed data).
- AUC_t will be calculated using the log-linear trapezoidal interpolation rule for extravascular model.
- The terminal elimination rate constant (λ_z) will be determined by log linear regression obtained on at least the 3 last quantifiable concentrations and will not include C_{max} ; $t_{1/2}$ is calculated by the program as $\ln 2/\lambda_z$;
- AUC_{∞} will be calculated by the program as: $AUC_{\infty} = AUC_t + AUC_{extrap}$ where last is the sampling time point of the last measurable concentration (t_{last}). AUC_{extrap} will be calculated by the program as: C_{last}/λ_z , where C_{last} is the observed concentration at time t_{last} and λ_z is the elimination rate constant during the apparent terminal elimination phase. AUC_{∞} will only be presented for participants with a reliable λ_z ;
- CL will be calculated by program as (molybdenum dose amount/ AUC_{∞});
- V_z will be calculated by the program as (molybdenum dose amount/ AUC_{∞})/ λ_z ;
- Dose normalized PK parameters will be calculated using the equivalent molybdenum dose and not the ALXN1840 dose. .

The following PK acceptance criteria will be applied to assess the reliability of elimination parameters:

- Number of points to calculate λ_z is greater than or equal to 3 excluding C_{max} point;
- The adjusted square of the correlation coefficient or coefficient of determination (Rsquare adjusted) for the goodness of fit of the regression line through the data points must be ≥ 0.90 ;
- $AUC_{extrap} \leq 20\%$.

Unreliable PK parameters will be listed but flagged and excluded from summary.

This document is confidential.

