9.5. Planned Statistical Models for PK Parameters and Concentrations

The primary analysis will be based on the PKDS-CO.

For the Period 1 and Period 2 comparisons, the PK parameters for total and PUF molybdenum (C_{max} , AUC_t , and AUC_{∞}) will be evaluated using an ANOVA statistical model with dosing period, treatment, and sequence as the fixed effects, and participant(sequence) as a random effect, using the natural logarithms of the data. Confidence intervals (CI, 90%) will be constructed for the least squares geometric mean ratio (GMR) for the 12 × 1.25 mg ALXN1840 mini-tablets versus a single 15 mg ALXN1840 tablet dose for all 3 PK parameters using the natural log-transformed data. The GMRs and the associated 90% confidence limits will be exponentiated back to the original scale.

The within-subject CV for the C_{max} , AUC_t , and AUC_{∞} will be estimated using the mean squared error from the ANOVA.

In addition, the geometric means and the associated 95% CIs of C_{max} , AUC_t , and AUC_{∞} will be reported for each treatment.

All secondary analyses will be based on the PKDS-E.

Dose-proportionality will be assessed across all EC mini-tablet treatments (2.5 mg, 5 mg, 10 mg, 15 mg, 30 mg ALXN1840) graphically and by using a power model (Smith, 2000; Newlands, 2006; EMA, 2010).

The following molybdenum dose-normalized PK parameters will be assessed for dose proportionality: C_{max_n} , AUC_{t_n} and AUC_{∞_n} . The log (PK parameters for plasma total and PUF molybdenum) will be included as a response variable and log (molybdenum dose) will be included as a fixed effect in the power model:

$$\log(\text{PK Parameter}) = \mu + \beta \cdot \log(\text{Molybdenum Dose})$$

*where $\beta = 1$ indicates perfect dose proportionality. Estimation of β , along with its 90% CI, will be provided.

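### Dietary molybdenum is left in the exposure data, so the dose-proportionality slope of an exactly proportional drug would read below 1, by an amount the documents leave open; a baseline-corrected sensitivity analysis should be pre-specified

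*Protocol*

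**What the plan says.** Protocol 4.2 says of both analytes: "Total Mo and PUF Mo concentrations also include physiologic molybdate concentrations from dietary micronutrient molybdate intake". Later sections do not use that fact.

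- **Basis of the parameters.** The introduction to SAP 9 says: "Calculations of individual PK parameters will be based on measured total molybdenum and, when feasible, PUF molybdenum concentrations". Protocol 9.4.3 says the same.
- **Pre-dose rule.** The only pre-dose rule for Mo is in SAP 9.3.1: values below the quantification limit "in pre-dose Day 1 samples will be treated as zero".
- **Power model.** In SAP 9.5, "log (molybdenum dose) will be included as a fixed effect in the power model", and it is the only term besides the intercept. The same section says "The following molybdenum dose-normalized PK parameters will be assessed for dose proportionality", yet gives a slope of 1 as perfect proportionality. The slope is reported with a 90% confidence interval, without acceptance limits.
- **Baseline.** SAP 7.2 defines a baseline for each dosing period. It is applied to copper and to safety data, not to Mo.
- **Quality screen.** SAP 9.4 requires at least 3 terminal points, adjusted R² of at least 0.90 and extrapolation of at most 20%. Then: "Unreliable PK parameters will be listed but flagged and excluded from summary".
- **Open clauses.** SAP 9.2 allows additional PK parameters and Protocol 9.4.1.2 foresees further proportionality methods. Neither specifies a baseline correction.

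**The concern.** An additive background matters little when two 15 mg treatments are compared, because both carry the same amount. It matters more across a 12-fold dose range. Randomization does not remove the effect, because the dose itself sets the background's share of exposure.

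The result at stake is the secondary objective. Dietary Mo could be read as less-than-proportional exposure to the mini-tablet over the doses that Protocol 4.3 links to the planned pediatric study.

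The planned checks are not built to catch this. The SAP 9.4 criteria concern elimination parameters, so they do not screen Cmax or AUCt. A background just under the 1.00 ng/mL limit would be recorded as zero in the Period 1 pre-dose sample while still adding to every later quantifiable concentration.

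**Working it through.** **Planning figures reproduced (Protocol 4.2 and 4.3).**
- Total Mo at 2.5 mg, from the anticipated Cmax of about 40 ng/mL: 40/2⁵ = 1.25 ng/mL after 5 half-lives, as stated.
- Ultrafiltrate (PUF) Mo: 2/2³ = 0.25 ng/mL after 3 half-lives, as stated.
- Washout: 1 − 2⁻⁷ = 99.2%, as stated. The implied half-life is 336 h / log₂(125) = 48.2 h.

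**Hand check at a background of 0.9 ng/mL.**
- Drug area at 2.5 mg ≈ Cmax/λz = 40/(ln 2/48.2) ≈ 2,782 ng·h/mL; at 30 mg, 12 times that, about 33,378.
- Background area over 336 h = 0.9 × 336 = 302. Its share is 302/2,782 = 10.9% at 2.5 mg and 302/33,378 = 0.9% at 30 mg.
- Dose-normalized ratio, 2.5 mg to 30 mg: 1.109/1.009 = 1.099. Two-point slope = 1 − ln(1.099)/ln(12) = 0.96.
- The full calculation gives 0.95, because the background also flattens the terminal phase and so inflates the extrapolated area.

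**Full calculation.** The profile is noise-free and exactly proportional, with the 20 planned sampling times, LLOQ 1.00 ng/mL and the SAP 9.4 rules. Assumed: constant background, absorption rate 0.5/h, lag 2 h, arm weights 12/12/12/48/12. The response is un-normalized, so the reference slope is 1.

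| Background (ng/mL, assumed) | Cmax slope | AUCt slope | AUC∞ slope | Extrapolated at 2.5 mg |
|---|---|---|---|---|
| 0 | 1.00 | 1.01 | 1.00 | 3% |
| 0.25 | 1.00 | 1.00 | 0.99 | 4% |
| 0.5 | 1.00 | 0.99 | 0.98 | 5% |
| 0.9 | 0.99 | 0.96 | 0.95 | 5% |
| 2 | 0.98 | 0.93 | 0.88 | 13% |

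Dose-normalized AUC∞ at 2.5 mg exceeds that at 30 mg by 2%, 14% and 35% at 0.25, 0.9 and 2 ng/mL. At 2 ng/mL the 2.5 mg profile still passes SAP 9.4 (extrapolation 12.6%, adjusted R² 0.98). The 20% limit is reached only near 3 ng/mL.

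**Sensitivity to inputs.** With half-life 40–60 h and Cmax 30–50 ng/mL at 2.5 mg, the AUC∞ slope is 0.985–0.991 at 0.25 ng/mL and 0.78–0.92 at 2 ng/mL.

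**Primary comparison.** A true AUC∞ ratio of 0.90 reads 0.905 at 2 ng/mL.

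**Which baseline to subtract.** After a 15 mg dose the proportional Cmax is 40 × 15/2.5 = 240 ng/mL. At most 240 × 0.008 = 1.9 ng/mL of it remains 14 days later. The Extension pre-dose sample can therefore hold decaying drug as well as background.
- Subtracting the Extension pre-dose value as a constant over-corrects the AUC∞ slope to about 1.06.
- Subtracting the Period 1 value, when it is quantifiable, gives 1.00 without carry-over and 0.98 with the maximum carry-over.
- When the Period 1 value is below 1.00 ng/mL, the substituted value drives the answer. AUC∞ slopes without carry-over:

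| True background (ng/mL) | Subtract 0 | Subtract LLOQ/2 | Subtract LLOQ |
|---|---|---|---|
| 0 | 1.00 | 1.02 | 1.04 |
| 0.25 | 0.99 | 1.01 | 1.03 |
| 0.9 | 0.95 | 0.98 | 1.00 |

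**The case against.** **The background may be low.** Protocol 4.2 places dietary molybdate in PUF Mo as well as total Mo. Protocol 4.3 anticipates a PUF Mo Cmax of only about 2 ng/mL at 2.5 mg, falling to 0.25 ng/mL. If dietary molybdate is ultrafilterable, a 2 ng/mL background would equal that whole Cmax, and anything above 0.25 ng/mL would prevent the stated fall. These are planning values, not measurements, so they do not settle the level, but they favour the end where the bias is negligible. This stands, and is why 0.88 is only an upper scenario.

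**No stated decision depends on it.** There is no acceptance range for the slope. In a simulation with assumed variability, the slope's SD was 0.045–0.050, so a 90% interval is about ± 1.645 × 0.045 to 0.050 = 0.07 to 0.08. The bias for backgrounds up to 0.9 ng/mL (0.01 to 0.05) lies inside that. This stands on importance. It does not remove a bias that always acts in one direction.

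**Below the LLOQ the correction is imputation.** This also stands: LLOQ/2 replaces an error of −0.01 with one of +0.01 at 0.25 ng/mL. It argues for reporting a range rather than choosing a value.

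**The data will be partly visible anyway.** SAP 9.3.3 says "Plasma concentration data will be summarized separately by time point for each treatment", and individual values are listed. A background could be noticed there, but a correction chosen afterwards would be post hoc, and the per-period baseline in SAP 7.2 would invite the over-correction shown above.

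**Conclusion.** The gap in the text is real: the protocol recognizes a dietary component and the plan does not account for it. The direction of the bias is certain for any constant positive background. Its size is not, because the endogenous level is not documented: for total Mo AUC∞ the slope falls from 1 to about 0.99 at 0.25 ng/mL, 0.95 at 0.9 ng/mL and 0.88 at 2 ng/mL. Cmax moves little. These figures rest on the planning Cmax ("for total Mo of approximately 40 ng/mL is anticipated after the lowest ALXN1840 dose of 2.5 mg"), the half-life implied by the washout statement, and a constant background.

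A reader might infer that the study will probably report false non-proportionality, or that the relative bioavailability result is compromised. The documents support neither: their ultrafiltrate figures point toward a small background if dietary molybdate is ultrafilterable, and the 15 mg versus 15 mg ratio barely changes. PUF Mo is not sized here. Protocol 4.2 calls it exploratory, although Protocol 3 lists it among the primary and secondary endpoints, and Protocol 4.3 already accepts possible extrapolation above 20% for it.

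This is an inexpensive improvement to the secondary analysis. The mismatch in SAP 9.5 between dose-normalized parameters and a reference slope of 1 is a separate, definite error.

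**What to change.** Before any Mo result is seen, including the interim in SAP 13, add one sensitivity analysis to SAP 9.4 and 9.5, beside the unchanged planned analysis:

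1. Repeat the noncompartmental analysis and power model after subtracting each participant's Period 1 pre-dose Mo from all of that participant's concentrations. That sample is drug-free because prior exposure is an exclusion criterion (Protocol 5.2). Set negative results to zero and then apply the SAP 9.3.1 rules.
2. If the Period 1 value is below LLOQ, report results for 0, LLOQ/2 and LLOQ as a range, with no preferred value.
3. Do not subtract the Extension pre-dose value as a constant.
4. Report pre-dose Mo as a percentage of Cmax by arm and period.

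Separately, amend SAP 9.5 and Protocol 9.4.1.2 to name the response and its matching reference slope: 1 for un-normalized parameters, 0 for dose-normalized ones.

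The cost is wording and one extra run; all samples are already planned. Noise rises slightly: the simulated SD of the AUC∞ slope goes from 0.045–0.050 to 0.048–0.052. The main limitation is that one fasted sample is applied to Extension profiles at least 28 days later (14 + 14). If post-dose background averaged 30% above the pre-dose level (assumed), the correction would be partial: 0.84 would move to 0.94 at 2 ng/mL, with carry-over included.

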9.4.1.1. Analyses of Primary Endpoint

The primary analysis will be based on the PK Set.

The PK parameters for total and PUF Mo (C_{max} , AUC_t , and AUC_{∞}) will be evaluated using an ANOVA statistical model with dosing period, treatment, and sequence as the fixed effects, and participant as a random effect, using the natural logarithms of the data. Confidence intervals (CI, 90%) will be constructed for the least squares geometric mean ratio (GMR) for the ALXN1840 12 × 1.25 mg versus single 15 mg ALXN1840 dose for all 3 parameters using the natural log-transformed data. The GMRs and associated 90% confidence limits will be exponentiated back to the original scale.

The within-participant CV for the C_{max} , AUC_t , and AUC_{∞} will be estimated using the mean squared error from the ANOVA. In addition, the geometric means and the associated 95% CIs of C_{max} , AUC_t , and AUC_{∞} will be reported for each treatment.

Detailed PK analyses will be described in the SAP.

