9.4.1.2. Analyses of Secondary Endpoints

All secondary analyses will be based on the PK Set.

Dose-proportionality will be assessed across all EC mini-tablet treatments (2.5 mg, 5 mg, 10 mg, 15 mg, 30 mg ALXN1840) graphically and by using a power model ([Smith, 2000](#); [Newlands, 2006](#); [EMA, 2010](#)). The following dose-normalized PK parameters will be assessed for dose proportionality: C_{max_n} , AUC_{t_n} and AUC_{∞_n} . The log (PK parameters for plasma total and PUF Mo) will be included as a response variable and log (dose) will be included as a fixed effect in the power model:

$$\log(\text{PK Parameter}) = \mu + \beta \cdot \log(\text{Dose})$$

where $\beta = 1$ indicates perfect dose proportionality. Estimation of β , along with its 90% CI, will be provided.

Additional approaches to test dose proportionality, such as an ANOVA model, will be explored ([Calvo, 2005](#)).

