5.1. Primary PK Endpoint

PK parameters for plasma total molybdenum and PUF molybdenum (C_{max} , AUC_t , and AUC_{∞})

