5.2. Secondary PK Endpoints

Dose-normalized PK parameters for plasma total molybdenum and PUF molybdenum (C_{max_n} , AUC_{t_n} , and AUC_{∞_n})

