5.4. Exploratory Endpoints

- CL/F, body weight, and BMI
- Absolute and percent changes from pre-dose baseline of plasma copper concentrations: total copper and PUF copper

This document is confidential.

6. Analysis Sets

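### Does the rationale sentence calling PUF Mo exploratory leave it unclear which results answer the primary objective?

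*Protocol*

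**What the plan says.** Protocol 4.2 explains why two analytes are measured. Total Mo cannot separate drug bound in the copper-albumin complex from free drug and its breakdown products, and PUF Mo is added to describe the unbound part. The section presents both as surrogates for drug exposure, says the pharmacokinetics of both will be characterized, and then ends: "The primary PK measure is total Mo, whereas PUF Mo is an exploratory measure".

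The sections that define endpoints and analyses rank the two equally:

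- **Primary endpoint.** The primary row of Protocol Table 4 gives "PK parameters for plasma total Mo and PUF Mo" (Cmax, AUCt and AUC∞), as does the synopsis. SAP 3 repeats the row, and SAP 5.1 lists "PK parameters for plasma total molybdenum and PUF molybdenum".
- **Primary analysis.** Protocol 9.4.1.1 opens its crossover ANOVA with "The PK parameters for total and PUF Mo". SAP 9.5 applies the same model to both analytes.
- **Secondary endpoint and analysis.** SAP 5.2 lists "Dose-normalized PK parameters for plasma total molybdenum and PUF molybdenum". For the power model, Protocol 9.4.1.2 states "The log (PK parameters for plasma total and PUF Mo) will be included as a response variable".
- **Exploratory endpoints.** PUF Mo enters only through clearance: "To explore relationships between total and PUF Mo clearance and body size" in Table 4, and "CL/F, body weight, and BMI" in SAP 5.4. Total Mo sits in the same objective.

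Protocol 9.1.1 names no analyte and states that no formal null hypothesis is tested. Protocol 9.4.3 and SAP 9 calculate PUF Mo parameters when feasible and give no rank. SAP 9.6 and SAP 14 record no departure from the protocol.

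**The concern.** Primary and exploratory are the words that head the rows of the objectives table, so a sentence using both to rank the analytes reads like a statement of endpoint hierarchy. Taken that way, it contradicts the table, and no text reconciles the two. The SAP claims conformity with a protocol that disagrees with itself.

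The possible stake is interpretation. The two analytes measure different things, so their formulation comparisons could point in different directions. The trial is open-label, and the relative-bioavailability results are read at an interim analysis that informs dosing in a planned pediatric study. If the rank of PUF Mo were truly open, someone could decide after seeing the results whether a discordant PUF Mo ratio belongs to the primary conclusion.

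**Working it through.** **Inputs**

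- Parameters per analyte: 3 (Cmax, AUCt, AUC∞), from Protocol 9.4.1.1.
- Analytes ranked primary: 1 under the 4.2 sentence; 2 under Table 4, Protocol 9.4.1.1, and SAP 5.1 and 9.5.
- Sample size: 48 enrolled, at least 40 completers, about 15% dropout (Protocol 9.2, SAP 4.3).
- Hypothesis, significance level, acceptance range: none (Protocol 9.1.1, SAP 9.5).

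**Step 1. The plan's own sample-size figure.** 40 / (1 − 0.15) = 47.06, rounded up to 48. This reproduces the stated number. Neither the number of analytes nor their rank enters the formula, and the protocol gives practicality and convention as the basis.

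**Step 2. Size of the inconsistency.**

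| Quantity | 4.2 sentence | Endpoint and analysis sections |
|---|---|---|
| Primary GMRs | 3 × 1 = 3 | 3 × 2 = 6 |
| Secondary power-model slopes | 3 × 1 = 3 | 3 × 2 = 6 |

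**Step 3. Does the count affect an error rate?** For illustration, treat the 90% intervals as independent (an assumption; the documents give no correlation). All 3 cover their true values with probability 0.9³ = 0.729, and all 6 with 0.9⁶ = 0.531. These figures would matter if the plan made a joint claim, for example that every interval must lie within limits. It makes none. Each interval is reported as a 90% interval for its own ratio, and that property does not depend on how many others are called primary.

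**Step 4. Does the count affect what is run?**

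- *Models.* SAP 9.5 specifies the same ANOVA and the same power model for both analytes.
- *Reliability rules.* The criteria in SAP 9.4 for λz and the 20% extrapolation limit apply to both alike.
- *Interim.* SAP 13 takes in all PK, PD and safety data and uses no endpoint rank.

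So 6 GMRs and 6 slopes are produced under either reading.

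**Step 5. Which text governs?** Protocol 9.4.1.1 and 9.4.1.3 leave the detailed PK analyses and the exploratory analyses to the SAP. SAP 5.1, 5.2 and 9.5 are unambiguous. SAP 10, the exploratory section, contains clearance against body size for both analytes and no PUF Mo Cmax or AUC. An exploratory status for those parameters therefore has no analysis section to live in. The statement of no change in SAP 9.6 and 14 is accurate when set against Table 4 and Protocol 9.4.1.

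**The case for a change.** The strongest case for acting runs as follows. With no hypothesis and no acceptance range, endpoint rank is the only prespecified guide to which results carry the primary conclusion. It should therefore be settled before the interim results are seen, and settling it costs only wording. Other text can be read as supporting a hierarchy: the washout is justified on total Mo, the pediatric simulations used total Mo, and PUF Mo parameters are calculated when feasible.

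The contradiction itself stands, and so does the count of three against six. The rest is weaker.

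- The washout sentence describes how fast total Mo leaves plasma. The simulations used data from earlier studies. Neither assigns a rank.
- The feasibility wording is a condition on whether a parameter can be calculated, and SAP 9.2 applies similar wording to both analytes.
- The lack of a rule for discordant results is a consequence of having no acceptance range, without which disagreement has no defined meaning. The same holds for Cmax against AUC within total Mo, and ranking PUF Mo would not settle that.
- Moving PUF Mo to exploratory throughout would edit many consistent sections to fit one sentence. It is also a debatable choice, since 4.2 itself explains that total Mo cannot isolate the free drug.

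**Conclusion.** The concern does not call for a change. One sentence in the Protocol 4.2 rationale is out of step with the synopsis, Table 4, Protocol 9.4.1.1 and 9.4.1.2, and SAP 3, 5.1, 5.2 and 9.5. On paper the difference is 3 or 6 primary GMRs and 3 or 6 secondary slopes. In practice it is nil: enrolment stays at 48, the models are the same, and all 6 GMRs and 6 slopes are reported with 90% intervals. An analyst working from the SAP would label both analytes primary without hesitation.

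This rests on two conditions, both true of the current documents: the study remains one of estimation with no acceptance range, and the SAP governs the analysis. If a joint equivalence claim were ever added, the set of primary parameters would start to matter. As planned, the sentence is a clerical slip that the sponsor can tidy at any convenient amendment, and the results are sound if it is left alone.
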